4.6. Treatment Beyond Disease Progression

Subjects will be permitted to continue trial treatment beyond RECIST v1.1 defined PD as long as they meet the following criteria:

- Investigator-assessed clinical benefit and no rapid disease progression
- Subject is tolerating study treatment
- Stable performance status
- Treatment beyond progression will not delay an imminent intervention to prevent serious complications of disease progression (e.g., CNS metastases, impending vital organ compromise)
- Subject provides written informed consent prior to receiving additional nivolumab and or ipilimumab treatment, using an informed consent form describing any reasonably foreseeable risks or discomforts, or other alternative treatment options. The decision to continue treatment beyond initial progression should be discussed with the PI.

Additionally, in cases where the majority of the disease is stable or responding, and progressing lesions can be controlled with local therapy (i.e. resection or radiotherapy), the patient may be continued on trial following local therapy.

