 - a. If the initial biopsy will be excisional, the excised tumor cannot be counted as a target lesion and there must be another lesion amenable to incisional, excisional, core or forceps biopsy. In this scenario, the second biopsy can only be excisional if the lesion to be excised is not a target lesion.
 - b. Cytology tumor specimens (e.g. from fine-needle biopsies, or drainage of pleural/pericardial or ascites fluid) are not acceptable. Biopsies of bone lesions that do not have a soft tissue component are also not acceptable (i.e. decalcified tumor samples are not acceptable).
- K. For female patients of childbearing potential and male patients with partners of childbearing potential, agreement (by patient and/or partner) to use a highly effective form(s) of contraception (i.e., one that results in a low failure rate [$<1\%$ per year] when used consistently and correctly) and to continue its use for 6 months after the last dose of trial therapy. Highly effective contraception is one with a failure rate of $<0.1\%$. Birth

control pills on their own do not achieve that rate.

- a. Women of childbearing potential must have a negative pregnancy test (serum or urine) within 72 hours of the start of study drug administration
 - b. Women who have recently given birth must no longer be breastfeeding
- L. Adequate hematologic and end-organ function, defined by the following laboratory results obtained within 14 days prior to the first study treatment:
- Neutrophils ≥ 1500 cells/ μL (without granulocyte colony-stimulating factor support within 2 weeks prior to Cycle 1, Day 1)
 - Platelets $\geq 75,000$ / μL (transfusion to achieve this level is not permitted within 2 weeks of the first study drug administration)
 - Hemoglobin ≥ 9.0 g/dL
 - Alanine aminotransferase (ALT) and aspartate aminotransferase (AST) ≤ 3 x institutional upper limit of normal (ULN) with the following exceptions: Patients with documented liver metastases: AST and/or ALT ≤ 5 x ULN
 - Serum bilirubin ≤ 1.5 x ULN (Patients with known Gilbert disease who have serum bilirubin level ≤ 3 x ULN may be enrolled)
 - Serum creatinine ≤ 1.5 x ULN or creatinine clearance ≥ 50 mL/min

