4.4. Duration of Therapy

In the absence of treatment delays due to adverse event(s), treatment may continue until one of the following criteria applies:

- 1 Disease progression (PD by RECIST 1.1 with exception discussed in section 4.6
- 2 Symptomatic deterioration of health status without objective evidence of disease progression. Every effort should be made to document objective progression of disease in such cases.
- 3 Unmanageable toxicity attributed to trial therapy (see section 4.9)
- 4 Development of intercurrent illness limiting the ability to comply with study or the development of uncontrolled concurrent illness that prevents further administration of treatment or confound the ability to interpret data
- 6 General or specific changes in the patient's condition rendering the patient unacceptable for further treatment in the judgment of the investigator
- 7 Patient request for discontinuation, patient withdrawal from study, or patient lost to follow up
- 8 Death
- 9 Study termination

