4.8. General concomitant therapy and management of safety concerns

4.8.1. Concomitant therapy

Additional anti-tumor therapies are prohibited during study treatment. The use of corticosteroids or other immunosuppressive medications will not be allowed during study therapy (unless used to treat a drug related adverse event). Low-dose steroid use (≤ 2 mg of dexamethasone or equivalent) as corticosteroid replacement therapy is allowed.

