Appendix 4: Immune-Related Response Criteria

INTRODUCTION

Increasing clinical experience indicates that traditional response criteria (e.g., Response Evaluation Criteria in Solid Tumors, Version 1.1 [RECIST v1.1] and World Health Organization [WHO]) may not be sufficient to characterize fully activity in the new era of target therapies and/or biologics. In studies with cytokines, cancer vaccines, and monoclonal antibodies, complete response, partial response, or stable disease has been shown to occur after an increase in tumor burden as characterized by progressive disease by traditional response criteria. Therefore, conventional response criteria may not adequately assess the activity of immunotherapeutic agents because progressive disease (by initial radiographic evaluation) does not necessarily reflect therapeutic failure. Long-term effect on the target disease must also be captured. The immune-related response criteria¹⁹ (irRC) are criteria that attempt to do that by enhancing characterization of new response patterns that have been observed with immunotherapeutic agents (i.e., ipilimumab). (Note: The irRC only index and measurable new lesions are taken into account.)

GLOSSARY

| Term | Definition |
|--------------|---|
| SPD | sum of the products of the two largest perpendicular diameters |
| Tumor burden | $SPD_{\text{index lesions}} + SPD_{\text{new, measurable lesions}}$ |
| Nadir | minimally recorded tumor burden |
| irCR | immune-related complete response |
| irPD | immune-related progressive disease |
| irPR | immune-related partial response |
| irSD | immune-related stable disease |
| irBOR | immune-related best overall response |

BASELINE ASSESSMENT USING irRC

Step 1. Identify the index lesions (five lesions per organ, up to ten visceral lesions and five cutaneous lesions).

Step 2. Calculate the SPD of all of these index lesions:

$$SPD = \sum_i (\text{Largest diameter of lesion } i) \times (\text{Second largest diameter of lesion } i).$$

POST-BASELINE ASSESSMENTS USING irRC

Step 1. Calculate the SPD of the index lesions.

Step 2. Identify new, measurable lesions ($\geq 5 \times 5$ mm; up to five new lesions per organ: five new cutaneous lesions and ten visceral lesions).

Step 3. Calculate the SPD of the new, measurable lesions.

Step 4. Calculate the tumor burden:

$$\text{Tumor burden} = \text{SPD}_{\text{index lesions}} + \text{SPD}_{\text{new, measurable lesions}}$$

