Step 5. Calculate the change in tumor burden relative to baseline and the change in tumor burden relative to nadir.

Step 6. Derive the overall response using the table below.

| Overall Response | Criterion |
|------------------|---|
| irCR | Complete disappearance of all lesions (whether measurable or not, and no new lesions) confirmed by a repeat, consecutive assessment ≥ 4 weeks from the date first documented |
| irPR | Decrease in tumor burden $\geq 50\%$ relative to baseline confirmed by a consecutive assessment ≥ 4 weeks from the date first documented |
| irSD | Criteria for irCR, irPR, and irPD are not met; does not require confirmation |
| irPD | Increase in tumor burden $\geq 25\%$ relative to nadir confirmed by a consecutive assessment ≥ 4 weeks from the date first documented |

irCR = immune-related complete response; irPD = immune-related progressive disease; irPR = immune-related partial response; irSD = immune-related stable disease.

DETERMINATION OF irBOR

Once a patient has completed all tumor assessments, his/her irBOR may be determined:

| Condition | irBOR |
|---|-------|
| At least one irCR | irCR |
| At least one irPR and no irCR | irPR |
| At least one irSD and no irCR and no irPR | irSD |
| At least one irPD and no irCR, no irPR, and no irSD | irPD |

irBOR = immune-related best overall response; irCR = immune-related complete response; irPD = immune-related progressive disease; irPR = immune-related partial response; irSD = immune-related stable disease.

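### The irRC rules do not say how to score a lesion resected or irradiated on trial, so local therapy can turn unconfirmed irPD into irSD and count toward irRC PFS and the stage-1 gate

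*Combined protocol and SAP*

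**What the plan says.** Section 4.6 (Treatment Beyond Disease Progression) first lists conditions for continuing after RECIST v1.1 progression. It then adds a further case, for disease that is mostly responding or stable: "progressing lesions can be controlled with local therapy (i.e. resection or radiotherapy), the patient may be continued on trial following local therapy". Section 4.4 ties its stopping rule to this, ending treatment at RECIST progression "with exception discussed in section 4.6". Section 4.8.1 states "Additional anti-tumor therapies are prohibited during study treatment" and names no exception.

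Appendix 4 notes that "The irRC only index and measurable new lesions are taken into account", and instructs the assessor to "Calculate the change in tumor burden relative to baseline and the change in tumor burden relative to nadir". irPR is a fall of at least 50% from baseline. irPD is a rise of at least 25% "relative to nadir confirmed by a consecutive assessment" at least 4 weeks later. irSD is the default: "Criteria for irCR, irPR, and irPD are not met; does not require confirmation".

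Section 8 has no event, censoring or non-evaluable rule for on-study local therapy. Appendix 3 deals with local treatment only when deciding whether a lesion is measurable at baseline. The authors did guard against a similar problem with biopsies: in Section 3.1, if the initial biopsy is excisional, "the excised tumor cannot be counted as a target lesion". Section 4.6 has no counterpart.

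The irRC results matter in two places. irRC ORR and PFS are secondary endpoints (Section 1.2), and Sections 4.1 and 9 let stage 2 open if at least one of the first 10 patients has an irRC response or irRC stability of at least 24 weeks.

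**The concern.** irRC classifies the patient by total burden. If the lesion that drove the rise is resected, it contributes nothing to the next sum. If it is irradiated, it may contribute less. Because irPD must be confirmed, the order of events matters: a first scan in the irPD range, local therapy, then a second scan below the threshold. As written, progression is never confirmed, no irRC PFS event is recorded, and the patient is irSD. The control of disease then comes at least partly from surgery or radiation but is counted for nivolumab plus ipilimumab.

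At stake are irRC PFS, irRC best response, and the stage-1 decision, where one patient can be enough.

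**Working it through.** **The plan's own figure.** Inputs from Section 9: 10 patients in stage 1, 40 in total, reject with 4 or more responses, ORR 5% against 19%. With one endpoint at both stages, P(reject) = sum over x = 1 to 10 of P[Bin(10,p) = x] × P[Bin(30,p) ≥ 4 − x]. This gives 0.1018 at p = 5% and 0.8574 at p = 19%, matching the stated 0.1 and more than 85% at the stated precision.

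**irPD to irSD.** The lesion sizes are assumed; the thresholds come from Appendices 3 and 4.
- Baseline: four 20x20 mm index lesions in two organs. SPD = 4 × 400 = 1600. RECIST sum = 80 mm.
- First scan (week 9 in the study calendar): one lesion is 45x25 mm = 1125. SPD = 1200 + 1125 = 2325; 2325/1600 − 1 = +45.3%, in the irPD range but unconfirmed. RECIST sum = 60 + 45 = 105 mm; 105/80 − 1 = +31%, +25 mm, which is PD.
- Section 4.6 condition: three of four lesions are stable, and they hold 1200/2325 = 52% of the burden.
- The lesion is resected. Next scan (week 18): SPD = 1200; 1200/1600 − 1 = −25%. irPD is not confirmed and irPR is not met, so the result is irSD.
- If nothing changes by the following scan (week 30, 12 weeks later), the patient has irSD beyond 24 weeks. The Appendix 4 best-response table gives irSD, and the gate is open.

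There is a small offset: the nadir is now 1200, so a later rise to 1500 (1.25 × 1200) would be in the irPD range.

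**When irPR could arise.** If the treated lesion held share s of baseline SPD and the rest stands at g times its baseline value, irPR needs (1 − s) × g ≤ 0.5, that is s ≥ 1 − 0.5/g.
- Rest unchanged (g = 1): s ≥ 50%.
- Rest down 10% (g = 0.9): s ≥ 44%.
- Rest down 20% (g = 0.8): s ≥ 37.5%.

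**Gate.** Let q be the assumed chance that one patient passes. P(open) = 1 − (1 − q)^10. With true RECIST ORR 5%, and every RECIST responder passing the gate, overall type I error = P[Bin(40, 0.05) ≥ 4] − (1 − q)^10 × P[Bin(30, 0.05) ≥ 4].

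| q | P(open) | Type I error |
|---|---|---|
| 5% | 40% | 0.102 |
| 10% | 65% | 0.117 |
| 15% | 80% | 0.126 |
| 20% | 89% | 0.132 |

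These rows show how sensitive the gate is to q. They do not estimate the effect of local therapy, because genuine irRC stability raises q as well.

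**The case against.** - **Section 4.6 is a specific exception to a general rule.** This is a fair reading, and Section 4.4 cites 4.6 in that way. A reader might infer a flat contradiction, but the text supports only a missing link: 4.8.1 is worded without exception and does not mention 4.6.
- **Later scans are outside the response basis.** The synopsis (Duration of Intervention and Evaluation) bases response on assessments up to investigator-assessed initial progression. This limits the problem but does not remove it. Section 5.2 sets the schedule without that cut-off, and irPD cannot be confirmed without a later scan.
- **Surgery alone cannot produce an irPR under 4.6.** This largely stands. With the rest unchanged, the treated lesion must have held at least half of baseline SPD. Having grown, it holds more than half of the current burden, so by burden most of the disease is not stable. The case survives if the majority is counted by number of lesions, or if the rest also shrank, in which case part of the fall is real.
- **The RECIST primary endpoint is not affected.** A reader might infer that it is inflated too. The local-therapy sentence sits under treatment beyond progression and follows the RECIST conditions, so on the natural reading RECIST PD comes first, as in the example. RECIST ORR is exposed only if 4.6 is read to allow local therapy before RECIST PD.
- **Opening the gate does not make the trial positive.** This is correct. Rejection still needs 4 or more responses on the RECIST primary endpoint.
- **A resected lesion scored as zero is an inference.** This is correct for Appendix 4, which is silent. An irradiated lesion would be scored at its measured size. The silence is itself the gap.

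**Conclusion.** The concern holds in a limited form. Applied as written, the irRC rules can convert a first, unconfirmed irPD into irSD through local therapy, which can inflate irRC PFS and satisfy the stage-1 gate. The effect requires the treated lesion to be an index or new measurable lesion, the therapy to fall before the confirming scan, and post-progression scans to be used. One converted patient changes the gate decision only if none of the other nine passes.

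The documents give no frequency of local therapy, so the bias cannot be sized; the lesion sizes and q values above are assumptions. The stronger conclusions, that irPRs will be created by surgery or that the primary RECIST result is compromised, are not supported. The correction is worth making because the rule is cheap to state before the data are seen and hard to defend afterwards.

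**What to change.** 1. Reconcile Sections 4.6 and 4.8.1 so that they give one instruction. Which clinical rule applies is for the investigators to decide.
2. In Section 8 and Appendix 4, state that assessments after on-study local therapy to a progressing lesion do not count toward CR/PR, irCR/irPR or stability of at least 24 weeks, including for the stage-1 gate.
3. For irRC PFS and duration of response, take the date on which the lesion was found to be progressing as the event date.
4. Report a sensitivity analysis using the irRC burden without this rule. This is needed because step 3 departs from the total-burden definition: it counts an event even where total burden rose by less than 25%. Censoring at local therapy is not a suitable alternative. The therapy is given because of progression, so the censoring would be informative and could favour the study drugs.

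The cost is a few sentences, recording the date and site of any local therapy, and one extra analysis. irRC results may look slightly less favourable.

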4.7. Duration of Follow Up

Patients who discontinue trial therapy will be followed for survival after removal from study until death.

4.8. General concomitant therapy and management of safety concerns

4.8.1. Concomitant therapy

Additional anti-tumor therapies are prohibited during study treatment. The use of corticosteroids or other immunosuppressive medications will not be allowed during study therapy (unless used to treat a drug related adverse event). Low-dose steroid use (≤ 2 mg of dexamethasone or equivalent) as corticosteroid replacement therapy is allowed.

4.8.2. Management of Safety concerns

Measures will be taken to ensure the safety of patients participating in this trial, including the use of stringent inclusion and exclusion criteria (section 3.1 and 3.2) and close monitoring (as indicated below and in Sections 5 and 6). See Section 6 for complete details regarding safety reporting for this study.

4.8.3. Monitoring

Safety will be evaluated in this study through the monitoring of all serious and non-serious AEs, defined and graded according to NCI CTCAE v4.0. (see appendix 1). Patients will be assessed for safety (including laboratory values) according to Section 5. Patients will be followed for safety for 100 days following the last dose of study treatment.

General safety assessments will include serial interval histories, physical examinations, and specific laboratory studies, including serum chemistries and blood counts (see Section 5 for the list and timing of study assessments). All SAEs and protocol-defined events of special interest (see Section 6) will be reported in an expedited fashion (see Section 6.5). In addition, investigators will review and evaluate observed AEs on a regular basis.

Patients who have an ongoing study treatment-related adverse event upon study completion or at discontinuation from the study will be followed until the event has resolved to baseline grade, the event is assessed by the investigator as stable, new anti-cancer treatment is initiated, the patient is lost to follow-up, the patient withdraws consent, or until it has been determined that study treatment or participation is not the cause of the AE.

4.8.4. Management for Immuno-Oncology Agent AEs

Immuno-oncology (I-O) agents are associated with AEs that can differ in severity and duration than AEs caused by other therapeutic classes. Nivolumab and ipilimumab are considered immuno-oncology agents in this protocol. Early recognition and management of AEs associated with immuno-oncology agents may mitigate severe toxicity. Please review the label/package insert for Management Algorithms developed to assist investigators in assessing and managing AEs.

4.8.5. Treatment of Nivolumab or Ipilimumab Infusion Reactions

Since nivolumab and ipilimumab contain only human immunoglobulin protein sequences, they are unlikely to be immunogenic and induce infusion or hypersensitivity reactions. However, if such a reaction were to occur, it might manifest with fever, chills, rigors, headache, rash, pruritus, arthralgias, hypo- or hypertension, bronchospasm, or other symptoms. All Grade 3 or 4 infusion reactions should be reported within 24 hours to the PI and reported as an SAE if criteria are met. Infusion reactions should be graded according to NCI CTCAE (Version 4) guidelines.

Treatment recommendations are provided below and may be modified based on local treatment standards and guidelines, as appropriate:

For Grade 1 symptoms: (mild reaction; infusion interruption not indicated; intervention not indicated)

Remain at bedside and monitor subject until recovery from symptoms. The following prophylactic premedications are recommended for future infusions: diphenhydramine 50 mg (or equivalent) and/or acetaminophen 325 to 1000 mg at least 30 minutes before additional nivolumab or ipilimumab administrations.

For Grade 2 symptoms: (moderate reaction requires therapy or infusion interruption but responds promptly to symptomatic treatment [e.g., antihistamines, non-steroidal anti-inflammatory drugs, narcotics, corticosteroids, bronchodilators, IV fluids]; prophylactic medications indicated for ≤ 24 hours)

Stop the nivolumab or ipilimumab infusion, begin an IV infusion of normal saline, and treat the subject with diphenhydramine 50 mg IV (or equivalent) and/or acetaminophen/paracetamol 325 to 1000 mg; remain at bedside and monitor subject until resolution of symptoms. Corticosteroid and/or bronchodilator therapy may also be administered as appropriate. If the infusion is interrupted, then restart the infusion at 50% of the original infusion rate when symptoms resolve; if no further complications ensue after 30 minutes, the rate may be increased to 100% of the original infusion rate. Monitor subject closely. If symptoms recur, then no further nivolumab or ipilimumab will be administered at that visit. Administer diphenhydramine 50 mg IV, and remain at bedside and monitor the subject until resolution of symptoms. The amount of study drug infused must be recorded.

For future infusions, the following prophylactic premedications are recommended: diphenhydramine 50 mg (or equivalent) and/or acetaminophen/paracetamol 325 to 1000 mg should be administered at least 30 minutes before nivolumab or ipilimumab infusions. If necessary, corticosteroids (up to 25 mg of SoluCortef or equivalent) may be used.

For Grade 3 or 4 symptoms: (severe reaction, Grade 3: prolonged [i.e., not rapidly responsive to symptomatic medication and/or brief interruption of infusion]; recurrence of symptoms following initial improvement; hospitalization indicated for other clinical sequelae [e.g., renal impairment, pulmonary infiltrates]. Grade 4: Life threatening; pressor or ventilatory support indicated)

Immediately discontinue infusion of nivolumab or ipilimumab. Begin an IV infusion of normal saline and treat the subject as follows: Recommend bronchodilators, epinephrine 0.2 to 1 mg of a 1:1000 solution for subcutaneous administration or 0.1 to 0.25 mg of a 1:10,000 solution injected slowly for IV administration, and/or diphenhydramine 50 mg IV with methylprednisolone 100 mg IV (or equivalent), as needed. Subject should be monitored until the investigator is comfortable that the symptoms will not recur. Nivolumab or ipilimumab will be permanently discontinued. Investigators should follow their institutional guidelines for the treatment of anaphylaxis. Remain at bedside and monitor subject until recovery of the symptoms.

In case of late-occurring hypersensitivity symptoms (e.g., appearance of a localized or generalized pruritus within 1 week after treatment), symptomatic treatment may be given (e.g., oral antihistamine or corticosteroids).

